13.4 Leucovorin

Leucovorin, also known as folinic acid or citrovorum factor is a chemically reduced derivative of folic acid. Leucovorin is readily converted to another reduced folate, 5,10-methylenetetrahydrofolate, which acts to stabilize the binding of fluorodeoxyuridylic acid to thymidylate synthase, thereby enhancing the inhibition of this enzyme. It is used to enhance the effects of fluoropyrimidines such as 5FU.

Supply and Supplier

The following information was taken from the prescribing information for Sagent Pharmaceutical's leucovorin calcium.

Leucovorin calcium is commercially available as a sterile, single-use vial containing either 100mg or 350mg each. Commercially available supplies of generic leucovorin calcium will be obtained from Sagent or another manufacturer and used for this study.

Preparation, Storage and Stability

The appropriate dose of leucovorin (see Section 7.1) should be reconstituted and diluted and stored according to the package insert provided by the manufacturer and according to local pharmaceutical regulations.

Dosage and Administration

See Section 7.1.

Adverse Events Associated with Leucovorin

Leucovorin should not be used for pernicious anemia and other megaloblastic anemias secondary to the lack of vitamin B12. A hematologic remission may occur while neurologic manifestations continue to progress.

Leucovorin enhances the toxicity of 5FU. When these drugs are administered concurrently in the treatment of advanced colorectal cancer, as they are in this study, gastrointestinal toxicities (particularly stomatitis and diarrhea) are observed more commonly and may be more severe and of prolonged duration. Seizures and/or syncope have been reported rarely in cancer patients receiving leucovorin, usually in combination with fluoropyrimidine administration, and most commonly in those with CNS metastases or other predisposing factors, however, a causal relationship has not been established.

Allergic sensitization, including anaphylactoid reactions and urticaria, has been reported following administration of leucovorin.

Drug Interactions

Folic acid in large amounts may counteract the antiepileptic effect of phenobarbital, phenytoin and primidone, and increase the frequency of seizures in susceptible pediatric patients.

14. STATISTICAL METHODS

14.1 Sample size analysis and accrual

The pathological complete response with traditional chemotherapy in pancreatic cancer is very low (no reported complete response in neoadjuvant studies). We aim to evaluate the complete response rate and the correlation with outcome. So we assume the pathological complete response in traditional chemotherapy to be 1%. We expect that the pathological complete response after 2 cycles of FOLFIRINOX therapy is about 10%. We plan to enroll 48 patients over a 24 months period. Assuming 90% of patients are evaluable for response, we will have 43 patients evaluable for pathological complete response. Patients will be considered non-evaluable and be replaced with new subjects per analysis datasets section below. With evaluable patients, we have 82% power detect a significant difference from the traditional chemotherapy with a 5% Type I error rate using a two sided one-sample test for proportion.

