6. PATIENT REGISTRATION

All patients will be registered with the Indiana University Simon Cancer Center (IUSCC) Clinical Trials Office (CTO). Regulatory files will be maintained by the CTO and applicable regulatory documents must be completed and on file prior to registration of any patients. Potential patients will be identified in the Oncology surgery clinic, endoscopy suite and pancreatic cancer referral program.

Patients who are interested in this study at the time of their work-up and appear to be eligible for this trial will undergo the Informed Consent Process and be screened for eligibility. The original signed IRB approved Informed Consent Document and completed eligibility checklist will be forwarded to the CTO designee for eligibility verification and registration in the OnCore[®] database.

The expected duration of subject participation is 8-10 months (including time for surgery and recovery). Accrual is expected to be approximately 2 patients per month at Indiana University for a yearly accrual of approximately 24 patients and a total accrual of 48 patients. The approximate time to complete study enrollment will be approximately 24 months.

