14.2 Analysis datasets

Population	Definition
Enrolled	This will comprise all patients who meet the eligibility criteria and are registered onto the study.
Efficacy Evaluable	This will comprise all patients who complete at least 2 treatments and either undergo at least one post-baseline assessment or die before any evaluation.
Not Evaluable for Efficacy	This will comprise of patients who do not complete 2 out of 4 treatments unless it is related to profound toxicity leading to treatment discontinuation.
Safety	This will comprise all patients that contribute data to the safety analysis. This population should be specifically defined in the protocol.

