14.3 Statistical analysis plan

Primary Outcome:

- Pathologic complete response: the proportion of the 48 patients having a pathologic complete response with a 95% confidence interval (using normal approximation) will be calculated.

Secondary Outcomes:

- *Safety:* Adverse events of grades 3, 4, 5 by the CTCAE v4.3 criteria for each category listed in section 2.1.6 will be summarized. The proportion of patients with each category of AE will be calculated with a 95% confidence interval. After the enrollment of the first 20 patients, we will evaluate the rate of surgical resection. If >6 patients are not able to proceed with surgery due to excessive toxicity or progression (not including occult metastatic peritoneal disease that was found during surgery and not on imaging) the study will discontinue due to unacceptable toxicity.

- *Ability of patients to undergo surgical resection after receiving neoadjuvant FOLFIRINOX*: the proportion of patients who are able to go through surgery among those who have resectable tumor will be calculated accompanied with a 95% confidence interval.
- *Rate of resectability* will be evaluated by determining the proportion of patients who are able to undergo surgery with resection of their primary tumor (R0 vs R1) resection. A 95% confidence interval will be constructed for the rate.
- *Disease free survival (DFS)*: DFS is defined as time from registration to evidence of tumor recurrence (including clinical deterioration related to the underlying pancreatic cancer, as assessed by the investigator) or death from any cause. Kaplan-Meier curve for DFS will be plotted. Median DFS time will be calculated accompanied with a 95% confidence interval.
- *Overall survival*: time from registration to death for 48 patients with right censoring will be analyzed using Kaplan-Meier estimate. Median survival time will be obtained accompanied with a 95% confidence interval.
- *Objective response rate*: proportion of patients with complete responses (CR) or partial responses (PR) after 4 cycles of FOLFIRINOX treatment will be constructed with a 95% confidence interval.
- *Disease control rate*: Proportion of patients with complete responses (CR), partial responses (PR), or stable disease (SD) after 4 cycles of FOLFIRINOX treatment will be obtained with a 95% confidence interval.

Tertiary Outcomes:

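### Section 14.1 powers on 43 evaluable patients and replaces non-evaluable ones with no target or cap, while section 14.3 divides pCR by 48 patients without naming an analysis set

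*Combined protocol and SAP*

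**What the plan says.** All references are to the combined protocol and SAP.

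- **Section 14.1, enrolment and power.** "We plan to enroll 48 patients over a 24 months period". With 90% assumed evaluable, "we will have 43 patients evaluable for pathological complete response". The 82% power is stated for the evaluable patients: pCR of 1% against 10%, with a two-sided 5% one-sample test for a proportion.
- **Section 14.1, replacement.** "Patients will be considered non-evaluable and be replaced with new subjects per analysis datasets section below". No number is given at which replacement stops, and no total after replacement.
- **Section 6.** The plan is for "a total accrual of 48 patients", with no separate allowance for replacements.
- **Section 14.2.** The Enrolled set is "all patients who meet the eligibility criteria and are registered onto the study". The Efficacy Evaluable set needs two or more treatments plus a later assessment, or death before one. The Not Evaluable set holds patients with fewer than two of the four treatments, except where profound toxicity ended treatment. No set is tied to an endpoint.
- **Section 14.3.** The primary result is "the proportion of the 48 patients having a pathologic complete response". Overall survival is "time from registration to death for 48 patients with right censoring". Neither line names a set.

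**The concern.** Discounting enrolment for non-evaluable patients and replacing those patients are two allowances for the same loss. A plan can use both, but only if it says what number replacement is meant to protect. Section 14.1 does not, and 14.3 then uses a number (48) that is not the powered evaluable number (43).

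The primary endpoint is at stake. Under 14.2, a patient who stops before the second treatment because of progression, death or withdrawal is not evaluable and so is replaceable. Such a patient is very unlikely to have a pCR. Replacing these patients and dividing by evaluable patients only would remove failures from the denominator and raise the reported rate. In an open-label single-arm trial where four or five pCRs are expected, the denominator should be fixed in writing before results are known.

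There is a second gap that does not depend on replacement. A patient who stops before two treatments for profound toxicity has too few treatments for the Efficacy Evaluable set, and the exception removes that patient from the Not Evaluable set.

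**Working it through.** **Inputs.** From 14.1: null rate 1%, alternative 10%, two-sided 5%, 48 enrolled, 90% evaluable. From section 6: accrual of 48 at about 2 per month. The plan does not name an exact test; the exact binomial is my choice.

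**Step 1: reproduce the stated power.** Evaluable: 48 × 0.90 = 43.2, so 43. Reject at 3 or more pCRs; P(X ≥ 3 | n = 43, p = 0.01) = 0.0092, below 0.025. Power = P(X ≥ 3 | n = 43, p = 0.10) = 0.8176. This matches 82%. An arcsine approximation (0.828) matches too; a normal test with null variance gives 0.906 and does not.

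**Step 2: what each reading implies.**

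| Reading | Registered patients needed | Power | Fit with the text |
|---|---|---|---|
| The 48 are all enrolled, no replacement | 48 | 81.8% on the 43 evaluable | Replacement sentence has no role |
| Replace until 43 are evaluable | 43/0.9 = 47.8, about 48 | 81.8% | Accrual stands; the evaluable denominator is 43, not 48 |
| Replace until 48 are evaluable | 48/0.9 = 53.3, so 53–54 | 87.1% (n = 48, p = 0.10) | Exceeds accrual; does not match 82%; this target is not stated |

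Under the third reading, 54/2 = 27 months of accrual against 48/2 = 24.

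**Step 3: bias if the 48 are evaluable patients after replacement.** Assume that no replaced patient has a pCR and that the rate among evaluable patients is 10%.

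- By fraction lost: bias = 10% − 10% × (1 − loss). At the plan's 10% loss this is 10% − 9% = 1.0 point. For an assumed loss of 5% to 20% it is 0.5 to 2.0 points.
- By number replaced, r: bias = 10 − 10 × 48/(48 + r). This gives 0.20 point for r = 1, 0.94 for r = 5 and 1.72 for r = 10.

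If the 48 are everyone enrolled, nobody leaves the denominator and the bias is zero.

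**Step 4: the denominator in the reported result.** Four pCRs are 4/43 = 9.3% (Wald 95% CI 0.6% to 18.0%) or 4/48 = 8.3% (0.5% to 16.2%).

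**Step 5: power with everyone in the denominator.** If 10% of evaluable patients have a pCR and the other 10% of enrolled patients count as non-pCR, the rate among all 48 is 0.9 × 10% = 9%. P(X ≥ 3 | n = 48, p = 0.09) = 0.8185. The upper tail under 1% is 0.0124, so the cut-off is still 3.

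**The case against.** The strongest reply is that the sections can be made to agree. The only evaluable number in the plan is 43, and the power sentence is tied to it. Replacing up to 43 evaluable needs about 48 registered, so 48 would be the expected enrolment and replacement would protect the 43. This stands as far as accrual goes. A reader might infer that replacement breaks the accrual total and requires 53–54 patients, but that needs a target of 48 evaluable, which the plan nowhere states. The reply does not rescue 14.3, because on this reading the 48 there is not the powered evaluable set, and the plan still does not say where replacement stops.

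A second reply is that the 48 most naturally means everyone enrolled: 14.1 and section 6 both use 48 for enrolment, and overall survival runs from registration. That also stands, and on that reading there is no bias. A reader might infer that the primary estimate will be inflated; the documents support only that it could be, on the less natural reading.

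Third, the effect is small. The relevant window runs only to the second treatment, day 15 of cycle 1 (section 7.1). One point compares with a Wald half-width of 1.96 × √(0.10 × 0.90/48) = 8.5 points. The cut-off of 3 pCRs is the same at n = 43, 48, 53 and 54, so if replaced patients have no pCR, the test result does not change. This is accepted; the issue is the estimate and its definition.

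Finally, making the Enrolled set primary departs from the powered population. That is a real choice, not pure editing. It agrees with the 48 already in 14.3, and Step 5 shows that it does not lower power.

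**Conclusion.** The point holds as an undefined denominator and an open-ended replacement rule for the primary endpoint. The 82% power figure is sound for 43 evaluable patients and needs no correction. The accrual of 48 is not contradicted in itself.

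The possible upward bias in pCR is about 0.2 point per replaced patient, and about 1 point at the plan's 10% loss. It arises only if the 48 are taken as evaluable patients after replacement, and it assumes that replaced patients have no pCR. It also treats the whole 10% loss as stopping before the second treatment for reasons other than profound toxicity, so 1 point is near the upper end at that loss.

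The gap for early toxicity stoppers follows directly from the definitions in 14.2 and needs no assumption about replacement. The effect is modest, but the endpoint is primary and the repair is cheap, so it should be made.

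**What to change.** - **Section 14.3.** State that the primary pCR proportion uses all eligible registered patients (Enrolled set, planned n = 48), that any replaced patient stays in the denominator, and that every patient without a pathology-confirmed pCR, including those not resected, counts as non-pCR. Report pCR in the Efficacy Evaluable set as a labelled sensitivity analysis.
- **Section 14.1.** Delete the replacement sentence, or limit it to reaching 43 evaluable patients within the total accrual of 48.
- **Section 14.2.** Place patients who stop before two treatments for profound toxicity in the Efficacy Evaluable set as non-responders.

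**Cost.** Protocol and SAP wording. The reported pCR may be slightly lower, because early stoppers count as non-pCR. By exact binomial, power for all 48 at 9% is still about 82%. No accrual increase is needed.

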14.2 Analysis datasets

Population	Definition
Enrolled	This will comprise all patients who meet the eligibility criteria and are registered onto the study.
Efficacy Evaluable	This will comprise all patients who complete at least 2 treatments and either undergo at least one post-baseline assessment or die before any evaluation.
Not Evaluable for Efficacy	This will comprise of patients who do not complete 2 out of 4 treatments unless it is related to profound toxicity leading to treatment discontinuation.
Safety	This will comprise all patients that contribute data to the safety analysis. This population should be specifically defined in the protocol.

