8. TOXICITIES TO BE MONITORED/DOSAGE MODIFICATIONS

Adverse events will be recorded for all patients beginning at C1D1 (i.e. start of neoadjuvant treatment) through 30 days post completion of neoadjuvant therapy or progression.

Each patient will be assessed for the development of any toxicity according to the Study Calendar (Section 10). Toxicity will be assessed according to the NCI Common Terminology Criteria for Adverse Events (CTCAE), version 4. Dose adjustments should be made according to the system showing the greatest degree of toxicity.

The treating physician may use his/her best clinical judgment when determining dose adjustments and/or holds. Dose adjustments of each agent may be made independently of dose modifications of the other agents (Table 3), and are based on the specific types of toxicities observed (Table 4). Agents held more than 14 days for toxicity should be discontinued. If more

than 2 dose reductions of a single agent in a patient are required, that agent will be discontinued. Once a dose reduction has been performed, no intra-patient dose re-escalation is permitted. Patients that have treatment delays for more than 14 days during any of the 6 cycles of chemotherapy should be removed from the study.

Additional detailed information on the potential adverse events and risks associated with each agent is included in Section 13.

Dose Level	Irinotecan	5FU Bolus / Infusion	Oxaliplatin	Leucovorin*
Starting dose (level 1)	180 mg/m ²	400/2400 mg/m ²	85 mg/m ²	400 mg/m ²
-1	150 mg/m ²	320/2000 mg/m ²	65 mg/m ²	400 mg/m ²
-2	120 mg/m ²	240/1600 mg/m ²	50 mg/m ²	400 mg/m ²

**If 5FU is discontinued, leucovorin is simultaneously discontinued.*

On Day 1 or Day 15	Toxicity at any point during cycle	Dose Level for Subsequent Administration		
Hematologic Toxicities				
If ANC <1.5 on the day of treatment, treatment will be delayed ² for 1 week. Resume treatment when ANC ≥1.5.	Neutropenia	Irinotecan	5FU	Oxaliplatin
	Grade 2	Maintain dose	Maintain dose	Maintain dose
	Grade 3	↓1 dose level	↓1 dose level	↓1 dose level
	Grade 4	↓2 dose levels	↓2 dose levels	↓2 dose levels
	Febrile neutropenia	↓2 dose levels	↓2 dose levels	↓2 dose levels
If platelets <75K on the day of treatment, delay ¹ treatment for 1 week. Resume treatment when platelets ≥75K.	Thrombocytopenia²	Irinotecan	5FU	Oxaliplatin
	≤Grade 1	Maintain dose	Maintain dose	Maintain dose
	Grade 2-3	↓1 dose level	↓1 dose level	↓1 dose level
	Grade 4	↓2 dose levels	↓2 dose levels	↓2 dose levels

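### The evaluability rule in 14.2 removes and replaces patients who fail before a second treatment, and 14.3 does not say which set the efficacy rates use

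*Combined protocol and SAP*

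**What the plan says.** - Section 14.2 defines the Efficacy Evaluable set as "all patients who complete at least 2 treatments and either undergo at least one post-baseline assessment or die before any evaluation". The death branch applies only once two treatments have been completed.
- The same table defines Not Evaluable for Efficacy as "patients who do not complete 2 out of 4 treatments unless it is related to profound toxicity leading to treatment discontinuation". It does not define profound, and it makes no exception for early progression or death.
- Section 14.1 makes these definitions the replacement rule: "Patients will be considered non-evaluable and be replaced with new subjects per analysis datasets section below". It also states "We plan to enroll 48 patients over a 24 months period" and "Assuming 90% of patients are evaluable for response, we will have 43 patients evaluable for pathological complete response", and bases the 82% power on the evaluable patients.
- Section 8 says "Patients that have treatment delays for more than 14 days during any of the 6 cycles of chemotherapy should be removed from the study". Footnote 1 to Table 4 instead discontinues the delayed agent and lets the others continue.
- Section 14.3 names none of the 14.2 sets for any endpoint. It gives 48 patients for pathologic complete response (pCR) and for overall survival, and no set for objective response or disease control.
- Footnote 2 of the Section 10 calendar gives every patient a surgical evaluation after completing or discontinuing chemotherapy.

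**The concern.** Whether a patient is kept or replaced depends partly on how that patient fares between the first and second treatments. A patient who fails in that interval is exchanged for a new one who can still succeed. A single-arm trial judged against a fixed 1% has no control arm in which the same exclusion would offset this.

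Early failure also bears on the questions the trial asks. Section 1.1 argues that preoperative treatment reveals aggressive biology before surgery, and Section 2.2 makes the fraction reaching surgery a secondary objective. For toxicity, an undefined adjective decides who is replaced, and that judgement is made after the event.

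**Working it through.** **Inputs.** From 14.1: null pCR rate 1%, expected rate 10%, 48 enrolled, 90% evaluable, 43 evaluable, two-sided 5% test, power 82%. Assumed, because the documents give no figures: 2 to 5 early failures replaced, and numerators of 5 pCRs, 36 resections and 42 patients with disease control. Five is 48 − 43, the plan's whole non-evaluable allowance, taken here as all early failures.

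**1. The plan's own figure.** 48 × 0.9 = 43.2, so 43. For an exact binomial with n = 43 and rate 0.01, P(X ≥ 2) = 0.0690 and P(X ≥ 3) = 0.0092. The smallest cut-off with an upper tail of at most 0.025 is 3. Power is P(X ≥ 3 | 43, 0.10) = 0.8176, which reproduces the 82%. At n = 48 it would be 0.8711, so the stated power rests on the 43.

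**2. Applying 14.2 patient by patient.**

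| Course | Efficacy Evaluable? | Not Evaluable? | Replaced? |
|---|---|---|---|
| Progression, deterioration or disease death after one treatment | No | Yes | Yes |
| Stops after one treatment, toxicity not judged profound | No | Yes | Yes |
| Stops after one treatment, toxicity judged profound | No | No, excepted | Not under the rule |
| Dies after two or more treatments, before evaluation | Yes | No | No |

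**3. Size with replacement.** With x successes, k replaced failures and 48 analysed, the reported rate is x/48 and the rate among all entered is x/(48 + k).

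| Outcome | Reported | k = 2 | k = 5 |
|---|---|---|---|
| pCR, x = 5 | 5/48 = 10.4% | 5/50 = 10.0% | 5/53 = 9.4% |
| Resection, x = 36 | 36/48 = 75.0% | 36/50 = 72.0% | 36/53 = 67.9% |
| Disease control, x = 42 | 42/48 = 87.5% | 42/50 = 84.0% | 42/53 = 79.2% |

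The gaps are 0.4 to 1.0 points for pCR, 3.0 to 7.1 for resection and 3.5 to 8.3 for disease control. Analysing 43 evaluable patients without replacement has a similar effect on pCR: 4/43 = 9.3% against 4/48 = 8.3%.

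**4. Size by fraction lost.** If a fraction f is dropped with no pCR among them, the reported rate is the all-patient rate divided by (1 − f). A true 10.0% reads 10.5% at f = 5% and 11.1% at the plan's own 10%. At an assumed 20%, beyond the plan's allowance, it reads 12.5%.

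**5. If some replaced patients do well.** With k = 5 and two of the five resected, the all-patient rate is 38/53 = 71.7%, a gap of 3.3 points. With four resected it is 40/53 = 75.5%, above the reported 75.0%. If all five had stable disease, disease control would be 47/53 = 88.7%, above 87.5%.

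**6. Effect on the test.** If the all-patient pCR rate is 1% and f = 10%, the rate in the evaluable set is 1.11%. The exact upper tail at 43 patients and cut-off 3 then rises from 0.0092 to 0.0122, still below 0.025.

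**7. Power if all dosed patients are analysed.** Take n = 48 and cut-off 3 (tail at 1% is 0.0124), with rate 10% × (1 − f):

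| f | Rate | Exact power |
|---|---|---|
| 5% | 9.5% | 84.7% |
| 10% | 9.0% | 81.9% |
| 15% | 8.5% | 78.6% |
| 20% | 8.0% | 75.0% |

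**The case against.** The strongest reply is that 14.3 never uses the Efficacy Evaluable set. It counts 48 patients for pCR and overall survival, and 48 is the planned enrolment. If that means everyone enrolled with nobody replaced, neither result is inflated. This stands as a possible reading, but it contradicts the replacement sentence and the 43-patient power basis in 14.1. It also leaves response and disease control without a set.

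A reader might infer that every removed patient is certain to miss pCR and resection, so that the bias can only be upward. The documents do not support this. A patient who stops early still has a surgical evaluation and entered with a tumour judged resectable (Section 4.1), so may be resected or have stable disease. Step 5 shows that the gap can shrink or reverse. Patients who progress or die early remain failures, so the expected direction is still upward.

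A reader might also infer that a patient with two treatments who withdraws alive falls in neither set. That is not established. Section 14.2 does not limit assessment to imaging, and the calendar schedules examination, performance status and laboratory tests on day 15.

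The number affected may be small. No imaging is scheduled between the first two treatments, so only clinically evident progression would count. One replaced failure moves resection only from 36/49 = 73.5% to 36/48 = 75.0%. For delays over 14 days, Section 11.5 lists them under unacceptable adverse events, which arguably brings them within the toxicity exception, and Table 4 footnote 1 does not make removal automatic. These passages conflict with one another and with Section 8 and must be reconciled. Finally, the exception may have been meant to keep toxicity failures evaluable. If so, it is a drafting gap, and it adds to the bias only if those patients are left out of the denominator.

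**Conclusion.** The point holds in a limited form and should be fixed. The text of 14.1 and 14.2 makes replacement depend on early outcome, leaves the toxicity cases to an undefined judgement, and places one-dose patients with profound toxicity in neither set.

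It does not follow that the trial's efficacy rates are all inflated. That depends on which denominator is used, and 14.3 does not settle it. Where the evaluable or replaced-in set is used, the expected bias is upward. Within the plan's 10% allowance it is about 1 point or less on pCR. On resection and disease control it is about 3 to 8 points, given the assumed numerators, 2 to 5 replaced failures, and none of those patients resected or controlled. It is smaller if some of them are.

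Nor is the primary test undermined: the stated 82% power is correct for 43 evaluable patients, and the error rate barely moves. The weakness is outcome-dependent exclusion together with an unnamed analysis set.

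**What to change.** 1. In 14.2, define the primary efficacy set as every eligible registered patient who receives at least one dose of FOLFIRINOX.
2. Count each patient by the actual pCR, resection or response result whenever it is observed, including after early discontinuation. Count the patient as non-pCR, not resected or not responding only when that result is not observed. Scoring every early stopper as a failure would misclassify those who are later resected.
3. Limit replacement to patients never dosed or found ineligible, and drop the profound-toxicity exception.
4. In 14.3, name this set for pCR, resection, objective response and disease control. State who the 48 are for pCR and overall survival, and reconcile that number with the 43 in 14.1.
5. Keep the two-treatment set as a sensitivity analysis.
6. Restate the 14.1 power on the new set: with 48 patients, about 82% if 10% are early failures, 79% at 15% and 75% at 20%.

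The cost is wording in 14.1 to 14.3. Reported rates become slightly less favourable, and the stated power may too if early failure exceeds 10%. Fewer patients would be replaced.
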